## SUMMARY OF CHANGES

Please refer to the comparison document for protocol Version 2.0 (dated 05 Jun 2023) versus protocol Version 3.0 (dated 22 Jan 2024) for actual changes in text. The summary of changes below is a top-line summary of major changes in the current DS2325-119 clinical study protocol (Version 3.0) by section.

### Amendment Rationale:

The main purpose of this amendment is to revise the dose administration frequency and add guidance for the evaluation of injection site reactions and minor clarifications throughout the document.

### CONVENTIONS USED IN THIS SUMMARY OF CHANGES

All locations (section numbers and/or paragraph/bullet numbers) refer to the current protocol version, which incorporates the items specified in this Summary of Changes document.

Minor edits, such as update to language that does not alter the original meaning, update to version numbering, formatting, change in font color, corrections to typographical errors, use of abbreviations, moving verbiage within a section or table, change in style, or change in case, are not noted in the table below.

Section # and Title	Description of Change	Brief Rationale
Protocol Synopsis: Study Objectives Section 2.1 Study Objectives	Modified the dose administration frequency to every other week for both primary and secondary objectives including the Main Phase and Extension Phase.	Change made to ensure consistency between dose administration frequency and study objectives.
Protocol Synopsis: Dosage Form, Dose and Route of Administration Section 1.4 Dose Selection and Justification of Dose Section 3.1.1 Overview	Modified the maintenance dose of 600 mg SC to be given biweekly. In addition, during both the Main Phase and Extension Phase, a 600 mg SC dose will also be given one week after the first dose of the phase, coinciding with one week before following biweekly doses.	Most patients find weekly visits too frequent to be compatible with their daily life commitments. Nonetheless, patients are inclined to accept an additional visit one week after the first dose of the Main Phase and Extension Phase, coinciding with one week before following biweekly doses.
Protocol Synopsis: Study Endpoints Section 2.3.3 Exploratory Endpoints Section 7.3 Biomarker Assessments	Corrected the endpoint from skin mRNA to skin concentration of mediators of skin inflammation.	Assessment of mRNA coding for mediators of skin inflammation and homeostasis is replaced by the direct assessment of these mediators as proteins.

Section # and Title	Description of Change	Brief Rationale
Protocol Synopsis: Study Endpoints Section 2.3.2 Secondary Endpoints Schedule of Events: Table 2 Appendix 16.3: Schedule of Events: Table 4	Corrected to epidermis-to-dermis DS-2325a concentration ratio instead of skin to plasma concentration ratio.	Clarification change.
Schedule of Events: Table 1 and Table 2 Appendix 16.3 Schedule of Events: Table 3 and Table 4	Modified the dose administration frequency to every other week. Modified the maintenance dose of 600 mg SC to be given biweekly. In addition, during both the Main Phase and Extension Phase, a 600 mg SC dose will also be given one week after the first dose of the phase, coinciding with one week before following biweekly doses.	Change made to ensure consistency between Schedule of Events tables and text.
Section 1.4 Dose Selection and Justification of Dose	Updated the area under the plasma concentration-time curve (AUC), maximum plasma concentration ( $C_{max}$ ), and $C_{ave}$ values	Change made in consideration of changed dose administration frequency.
Section 1.4 Dose Selection and Justification of Dose	Updated half-life values in healthy subjects for the 1000 mg IV dose and 600 mg SC dose.	Changes made to be consistent with the DS2325-104 CSR.
Section 4.2 Exclusion Criteria 4.2.1 Screening	Systemic treatment (#15) timeline updated to within 4 weeks before Screening.	4 weeks is deemed sufficient instead of 8 weeks.
Section 4.2 Exclusion Criteria 4.2.2 Baseline (Main Phase-Interventional Part)	Updated the Systemic treatment (#6) timeline to within 4 weeks before Baseline.	4 weeks is deemed sufficient instead of 8 weeks.
Section 5.6 Concomitant Medications	Corrected the header to "Concomitant Medications". Added clarification on the occasional and temporary use of corticosteroids.	Clarification change.
Section 5.7.2 Withdrawal Procedures	Minor clarification to withdrawal procedure.	Clarification change.

Section # and Title	Description of Change	Brief Rationale
Section 5.9 Dose Reduction	Minor edits to the frequency of dose administration.	Change made in consideration of changed dose administration frequency.
Protocol Synopsis: Study Endpoints Section 2.3.1 Primary Endpoint Section 8.1 Assessment of Safety Endpoints Section 8.4 Injection Site Reactions	Added a new section with instructions for patients and investigators on how to record injection site reactions as AEs.	Added section to increase accuracy, with the provision of evaluation guidance, of the recording of injection site reactions as AEs.
Section 8.9 Clinical Laboratory Evaluations	Deleted assessments of direct bilirubin and BUN.	Clarification change.
Schedule of Events: Table 1 and Table 2; footnote #6 Section 9 Efficacy Assessments Section 9.5 Skin Concentrations of Mediators of Skin Inflammation and Homeostasis Appendix 16.3 Schedule of Events: Table 3 and Table 4; footnote #6	Updated to provide clarification on the parameters that will be assessed to understand efficacy.	Changes made given that assessment of mRNA coding for mediators of skin inflammation and homeostasis is replaced by the direct assessment of these mediators as proteins.
Section 10.1 General Statistical Considerations	Included efficacy endpoint in the Baseline value for the last non-missing measurement before the first dose of the study drug.	Clarification change.
Section 10.4.5.1 Adverse Event Analyses	Added adverse event collection and analysis for injection site reactions.	Changes made in consideration of the added Section 8.4.
Section 10.2 Analysis Sets Section 10.3 Study Population Data	Added a definition for the All Enrolled Subject Set.	Required for summary analysis based on the Observational Part set of patients.

## PROTOCOL SYNOPSIS

EU CT Number:	2022-502853-32-00
IND Number:	157483
Protocol Number:	DS2325-119
Investigational Product:	DS-2325a
Active Ingredient(s)/INN:	DS-2325a
Study Title:	A Phase 1b/2, Double-Blind, Placebo-Controlled, Randomized, Parallel-Arm Study to Explore Safety, Pharmacokinetics, and Early Clinical Signal of Efficacy of DS-2325a in Patients with Netherton Syndrome
Study Phase:	Phase 1b/2
Indication Under Investigation:	Netherton Syndrome (NS)
Study Objectives:	
Observational Part
 
Objectives:
 

To explore the characteristics of patients with NS for 12 weeks immediately before study treatment administration by assessing the same safety and efficacy (including mechanistic efficacy) endpoints to be assessed during the Interventional Part.

 
Interventional Part
 
Primary Objective:
 

To explore the safety and tolerability of DS-2325a in patients with NS by administering DS-2325a every other week for 12 consecutive weeks (Main Phase) and to confirm by administering for an additional 24 weeks (Extension Phase).

 
Secondary Objectives:
 

To explore the pharmacokinetic (PK) properties of DS-2325a in patients with NS by administering DS-2325a every other week for 12 consecutive weeks (Main Phase) and to confirm by administering for an additional 24 weeks (Extension Phase).

To explore the efficacy of DS-2325a in patients with NS by administering DS-2325a every other week for 12 consecutive weeks (Main Phase) and to confirm by administering for an additional 24 weeks (Extension Phase).

To explore the immunogenicity of DS-2325a in patients with NS by administering DS-2325a every other week for 12 consecutive weeks (Main Phase) and to confirm by administering for an additional 24 weeks (Extension Phase).

	
Exploratory Objective:
 
 
To explore the mechanistic efficacy of DS-2325a in patients with NS by administering DS-2325a every other week for 12 consecutive weeks (Main Phase) and to confirm by administering for an additional 24 weeks (Extension Phase).
 

Study Design:	
The study follows a double-blind, placebo-controlled, randomized, parallel-arm design.
 
The study includes 2 parts: An Observational Part and an Interventional Part.

Study Duration:	
The total study duration from first patient-in to last patient-out is expected to be 72 weeks, including Enrollment (expected to take 16 weeks), Observational Part (12 weeks), the entire Interventional Part, ie, both Main Phase (12 weeks) and Extension Phase (24 weeks), and Follow-Up (8 weeks).
 
The duration including Enrollment, Observational Part, and the Interventional Part Main Phase, ie, until early clinical signal (ECS) readout, will be 40 weeks.
 
Each patient will be involved in the study for the total of 56 weeks (12 weeks Observational Part + 12 weeks Interventional Main Phase + 24 weeks Extension Phase + 8 weeks Follow-Up), excluding up to 4 weeks of screening.

Study Sites and Location:	This study will be conducted at a single site in France.
Patient Eligibility Criteria:	
Key Inclusion Criteria:
 
 
Male or female patients aged 18 to 65 years with clinical diagnosis of NS including at least 3 out of the 4 following clinical criteria: 
 
Neonatal erythroderma
 
Bamboo hair and/or alopecia
 
Chronic atopy specified as food allergy and/or asthma and/or rhino-conjunctivitis and/or eczema for at least 2 years
 
Ichthyosis linearis circumflexa or scaling erythroderma or equivalent.
 
 
 
 
Eligible patients are those who have received ineffective or otherwise inappropriate standard-of-care treatment and therefore remain in need of cure.
 
 
Immunohistochemistry documentation of absence of lympho-epithelial Kazal-type-related inhibitor (LEKTI) in the skin or confirmed serine peptidase inhibitor of Kazal type 5 (SPINK5) gene mutations.
 
NS involvement of <math>\geq 20\%</math> of Body Surface Area (BSA) at both Screening and Baseline.
 

- 
- Patients must give written informed consent to participation in the study prior to Screening.
  - Patients must be willing to have skin tape harvests collected from lesional and non-lesional skin areas.

Key Exclusion Criteria:

- Any skin disease that may interfere with the diagnosis or evaluation of NS.
- Any infection requiring treatment with systemic antibiotics, antivirals, antiparasitics, or antifungals within 2 weeks before Screening visit.

---

Dosage Form, Dose and Route of Administration:

DS-2325a will be provided as a sterile solution in CCI [REDACTED]. Placebo will be prepared from normal saline solution. Treatment will be given according to the maximum feasible dosing regimen of a single initial (“loading”) dose of 1000 mg IV followed by biweekly (“maintenance”) doses of 600 mg SC. However, during both Main Phase and Extension Phase, a 600 mg SC dose will also be given one week after the first dose of the phase, coinciding with one week before following biweekly doses. Thus, DS-2325a will be given at Weeks 1, 2, 3, 5, 7, 9, etc. Both 1000 mg and 600 mg doses were found to be safe and well-tolerated based on Phase 1a preliminary results.

---

Study Endpoints:

**Observational Part**

The same safety and efficacy (including mechanistic efficacy) endpoints to be assessed during the Interventional Part.

**Interventional Part**

Primary endpoints:

Safety endpoints will be adverse events (AEs), including serious AEs (SAEs), injection site reactions (ISRs), physical examination findings, vital sign recordings (body temperature, blood pressure, heart rate, respiratory rate), results of safety laboratory analyses of blood and urine, and electrocardiogram (ECG) findings.

Secondary endpoints:

Endpoints descriptive of plasma PK properties will be PK parameters derived from population PK analysis, including, but not limited to, pre-dose trough concentration ( $C_{trough}$ ),  $AUC_{tau,ss}$ , total body clearance (CL), and CL/F, and epidermis-to-dermis DS-2325a concentration ratio ( $K_{ed}$ ).

DS-2325a presence will be assessed in the skin if the optional skin biopsies will be available.

Endpoints for the assessment of efficacy (ECS) will include Ichthyosis Area Severity Index (IASI) (including IASI-Erythema and IASI Scaling), and Investigator Global Assessment (IGA) and patient-reported outcome (PRO) measures, such as Itch Numerical Rating Scale (NRS) scores and quality-of-life

[figure not shown]
---

---

	
assessments obtained using the Skindex-29, and the Dermatology-Life-Quality-Index (DLQI) questionnaires.
 
Anti-drug antibodies (ADAs) against DS-2325a will be the immunogenicity endpoint.
 
Exploratory endpoints:
 
Endpoints for the assessment of mechanistic efficacy will include transepidermal water loss (TEWL); skin concentration of mediators of skin inflammation and homeostasis, such as S100A7, S100A8, S100A9 and IL-36<math>\gamma</math>; skin KKL5 activity; and circulating cytokines, such as interleukin (IL)-36<math>\gamma</math>, IL-1<math>\beta</math>, IL-4, IL-6, IL-8, TSLP, and TNF<math>\alpha</math> and chemokines like CCL17 (TARC), CCL20 (MIP3A), CCL22 (MDC), and CCL27 (CTACK); and circulating immunoglobulin (Ig) E.

Planned Sample Size:	
The planned sample size is 9 to 12 patients with NS.
 
In the Interventional Part Main Phase, patients will be randomized to 2 parallel arms to receive DS-2325a or placebo in a 2:1 ratio. In the Extension Phase, all patients will receive DS-2325a.

Statistical Analyses:	
All efficacy analyses will be based on the modified Intent-to-Treat Analysis Set (mITT). The efficacy endpoints (IASI, IGA, patient-reported outcome [PRO] measures, and mechanistic endpoints) will be summarized by treatment group using descriptive statistics. Comparison between treatment groups for the change from Baseline (pre-treatment on Day 1 of Week 1 of the Interventional Part Main Phase) or from pre-treatment obtained by grouping Observational Part timepoints, which precede Baseline, to each post-treatment visit in IASI, IGA, PRO measures, and mechanistic endpoints will be summarized.
 
All safety analyses will be based on the Safety Analysis Set. All AEs will be coded using the Medical Dictionary for Regulatory Activities (MedDRA). Incidence summary of patients with treatment-emergent AEs will be presented by maximum severity, SAEs, AEs assessed as related to study, and AEs resulting in discontinuation of study drug. Observations at each visit and changes from Baseline in vital sign recordings, results of laboratory analyses, and ECG findings will be numerically summarized by treatment group over time. Physical examination findings at each evaluation will be listed and clinically significant abnormal findings will be noted in the listings.
 
All PK analyses will be based on the PK Analysis Set. Plasma concentration of DS-2325a will be summarized using descriptive statistics by treatment group and by phase. The PK parameters for both the Main Phase and the Extension Phase of the Interventional Part of study will be analyzed by descriptive statistics, including the mean, geometric mean, standard deviation (SD), coefficient of variation percentage (CV%) or median, minimum, and maximum.

---

**STUDY SCHEMA**

ECS = Early Clinical Signal

## SCHEDULE OF EVENTS

**Table 1: Visit Schedule for Observational Part and Interventional Part-Main Phase**

Schedule of Events		Observational Part			Interventional Part-Main Phase						
	Screening*				Baseline^						
Week	-4 to 0	1	5	9	1	2	3	5	7	9	11
Visit Window allowed (day)		±2	±2	±2	±1	±1	±1	±2	±2	±2	±2
Informed Consent	X										
Demographics, height, and BMI	X										
Body weight	X	X	X	X	X			X		X	
Eligibility Criteria	X				X						
Serology (HBV, HCV, and HIV)	X										
COVID-19 test	X				X						
Urine drugs of abuse	X										
Medical History	X										
Adverse Events (1)	X	X	X	X	X	X	X	X	X	X	X
Concomitant Medications (1)	X	X	X	X	X	X	X	X	X	X	X
Vital Signs (1)	X	X	X	X	X	X	X	X	X	X	X
Physical Exam (2)	X	X	X	X	X		X	X	X	X	X
Safety Laboratory Tests, Including Urinalysis (3)	X	X			X			X		X	
ECG (4)	X				X			X		X	
Serum Pregnancy Test	X										
Urine Pregnancy Test (5)					X			X		X	
Clinical Evaluations (IASI, IGA, and PRO) (2)	X	X	X	X	X		X	X	X	X	X
Skin Photography (2)	X	X	X	X	X		X	X	X	X	X
Mechanistic Evaluations (PD biomarkers) - TEWL (6)		X			X						
Mechanistic Evaluations (PD biomarkers) - Skin Tape Harvests (6)		X			X						
Mechanistic Evaluations (PD biomarkers) - Blood (7)		X	X	X	X			X		X	
Randomization					X						
Dose Administration (8)					X	X	X	X	X	X	X
PK (blood) (9)					X (10)		X	X	X	X	X
ADA (blood) (11)					X			X		X	

Abbreviations: ADA = Anti-drug Antibody, BMI = Body Mass Index, COVID-19 = Coronavirus Disease 2019, ECG = Electrocardiogram, EOS = End of Study, EOT = End of Treatment, HBV = Hepatitis B virus, HCV = Hepatitis C virus, HIV = Human Immunodeficiency Virus, IASI = Ichthyosis Area Severity Index, IGA = Investigator Global Assessment, IP = Interventional Part, IV = intravenous, OP = Observational Part, PD = Pharmacodynamics, PK = Pharmacokinetics, PRO = Patient-Reported Outcome, SC = subcutaneous, TEWL = Transepidermal water loss

\*Screening will occur during the 28 days preceding Week 1 of OP; ^Baseline is pretreatment on Day 1 of Week 1 of Interventional Part Main Phase

- (1) To be recorded at Screening; at Weeks 1, 5, and 9 during OP; every other week during IP before dose administration; and at Weeks 37 EOT and 45 EOS.
- (2) To be performed at Screening; at Weeks 1, 5, and 9 during OP; every other week (ie, at odd-numbered weeks, to start with Week 1) during IP before dose administration; and at Weeks 37 EOT and 45 EOS (except clinical evaluations [IASI, IGA, and PRO] and skin photography, which will not be performed at Week 45 EOS).
- (3) To be performed at Screening; at Week 1 during OP; at Weeks 1, 5, 9, 13, 21, and 29, during IP before dose administration; and at Weeks 37 EOT and 45 EOS.
- (4) To be performed at Screening; at Weeks 1, 5, 9, and 13 during IP before dose administration; and at Weeks 37 EOT and 45 EOS.
- (5) To be performed at Weeks 1, 5, 9, 13, 17, 21, 25, 29, and 33 during IP before dose administrations; and at Week 37 EOT.
- (6) To be performed at Week 1 during OP and at Weeks 1, 13, and 25 during IP before dose administration; and at Week 37 EOT. Skin tape harvests will allow assessing the skin concentrations of mediators of skin inflammation and homeostasis and skin KKL5 activity.
- (7) To be performed at Weeks 1, 5, and 9 during OP; at Weeks 1, 5, 9, 13, 21, 25, and 29 during IP before dose administration; and at Week 37 EOT.
- (8) To be given at Weeks 1, 2, and 3 and every other week during IP-Main Phase. Dose administration will be IV at Week 1 and then SC.
- (9) To be collected every other week (ie, at odd-numbered weeks, to start with Week 1) during IP before dose administration; and at Weeks 37 EOT and 45 EOS. Blood samples will be collected no more than 1 hour before the start of dose administration.
- (10) On Week 1 of IP, PK blood sample will also be collected at the end of infusion (ie, 1 hour after start of dose administration) and 1 hour later (ie, 2 hours after start of dose administration). These two blood samples will be collected  $\pm$  10 minutes from the nominal times.
- (11) To be collected at Weeks 1, 5, 9, 13, 17, 21, 25, 29, and 33 during IP before dose administration; and at Weeks 37 EOT and 45 EOS.

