## 1.2. Data Summary

CCI

CCI

To assess the general toxicity profile of DS-2325a, two 4-week intermittent SC dose toxicity studies were conducted, one in mice (CCI) and one in cynomolgus monkeys (CCI), with an 8-week recovery period at the dose levels of 0 (control group), CCI. A 26-week intermittent SC dose toxicity study was also conducted in mice (Q2D, 91 times in total) with an 8-week recovery period at the dose levels of 0 (control group), CCI. In all these studies, no toxicologically significant changes were noted in any animal at dose levels up to CCI included. Therefore, the no observed adverse effect level (NOAEL) of DS-2325a in these studies was considered to be CCI. Additionally, in telemetered male cynomolgus monkeys treated with a single SC dose of DS-2325a, no effects on the cardiovascular system, the respiratory system or the central nervous system were observed at dose levels up to CCI included.

In a cytokine release assay using human peripheral blood mononuclear cells in solid phase, DS-2325a induced higher levels of TNF compared with vehicle control. The extent of induction was less than that of bevacizumab, a reference antibody, for which low incidence of infusion-related reactions has been reported. In cytokine release assays using human peripheral blood mononuclear cells or human whole blood in liquid phase, DS-2325a did not induce the release of any cytokine tested compared with vehicle control. DS-2325a did not show cell proliferation activity in any assay. Therefore, the risk of infusion-related reactions upon DS-2325a administration is considered to be low given the results of these assays.

For further details, please refer to the current Investigator's Brochure (IB).

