## **2.3. Study Endpoints**

### **2.3.1. Primary Endpoint**

The primary endpoints of this study are:

- Safety endpoints, ie, AEs, including serious AEs (SAEs), injection site reactions (ISRs) physical examination findings, vital sign recordings (body temperature, blood pressure, heart rate, respiratory rate), results of safety laboratory analyses of blood and urine, and ECG findings.

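### No vital-sign reading is scheduled after dosing starts on the day of the 1000 mg IV infusion; the next is at Week 2, although PK blood is drawn 1 h and 2 h after the start

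*Combined protocol and SAP*

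**What the plan says.** - **Timing of vital signs.** In the Schedule of Events (Table 1, repeated in Tables 2 to 4), footnote (1) covers vital signs, adverse events and concomitant medications: "To be recorded at Screening; at Weeks 1, 5, and 9 during OP; every other week during IP before dose administration". It then adds the Week 37 and Week 45 visits, when no dose is given.
- **Week 1 of the IP.** The Vital Signs row has a single entry in this column. The synopsis describes a "single initial (“loading”) dose of 1000 mg IV followed by biweekly (“maintenance”) doses of 600 mg SC", and footnote (8) gives the route by week: "Dose administration will be IV at Week 1 and then SC".
- **PK on the same day.** Footnote (10) states that a "PK blood sample will also be collected at the end of infusion (ie, 1 hour after start of dose administration) and 1 hour later", that is, 2 hours after the start, each within 10 minutes of nominal.
- **Status of vital signs.** Section 2.3.1 lists among the primary safety endpoints "vital sign recordings (body temperature, blood pressure, heart rate, respiratory rate), results of safety laboratory analyses of blood and urine, and ECG findings".
- **Measurement and analysis.** Section 8.10 gives posture, rest time and parameters, with no timing relative to dosing. Section 6.2.3 says only that vital signs are recorded. Section 10.4.5.3 summarises them by scheduled time and arm, with change from the last value before the first dose.
- **Infusion reactions.** Section 1.2 reports that in a solid-phase assay "DS-2325a induced higher levels of TNF compared with vehicle control". It adds that the effect was smaller than with a reference antibody, that liquid-phase assays showed no cytokine release, and that the risk of infusion-related reactions is judged low.

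**The concern.** The loading dose is the largest single dose, the only one given intravenously, and falls in the only double-blind, placebo-controlled phase. Placebo patients also receive an infusion at that visit, so a controlled look at acute changes in blood pressure, heart rate, respiratory rate and temperature is possible once in the study. The schedule does not use it. The Week 1 reading is the reference for every later change, so infusion day itself contributes no change value in either arm.

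What is at stake is what a primary endpoint component can show. A table of vital-sign changes by arm could look unremarkable because nothing happened, or because nobody recorded a number until about a week later. The table cannot separate the two. The Week 1 ECG does not help, since footnote (4) also places it before the dose.

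**Working it through.** The plan gives no figure to reproduce. It plans no formal tests, and Section 10.5 does not base the sample size on power. The check is therefore a count of visits and intervals from Tables 1 and 2.

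**Inputs**
- Dosing visits, Main Phase: Weeks 1, 2, 3, 5, 7, 9, 11 = 7.
- Dosing visits, Extension Phase: Weeks 13, 14, 15, 17, 19, 21, 23, 25, 27, 29, 31, 33, 35 = 13.
- Vital-sign visits: all of these plus Weeks 37 and 45.
- Visit window at Weeks 1 and 2: ±1 day each.
- Post-infusion PK: 1 h and 2 h after the start of infusion.

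**Counts**
1. IV doses: 1, at Week 1. The other 7 + 13 − 1 = 19 dosing visits are SC and do not bear on an infusion question.
2. Vital-sign visits in the IP and follow-up: 7 + 13 + 2 = 22.
3. Vital-sign visits after the infusion: 22 − 1 = 21.
4. Scheduled vital-sign readings between the start of infusion and the 2 h PK sample: 0. Later the same day: 0.

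**Time from infusion to next reading**
- Nominal: 7 × (2 − 1) = 7 days.
- Each visit using its own window in full: 7 − 1 − 1 = 5 to 7 + 1 + 1 = 9 days.
- If the Week 2 window is instead counted from the actual Week 1 date: 7 − 1 = 6 to 7 + 1 = 8 days.

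**What reaches the analysis**
- Week 1 pre-dose value: Baseline, change zero by definition.
- 1 h and 2 h after the start: PK only, no vital-sign time point.
- Week 2: first change from Baseline, about 7 days after the infusion.

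**Footnote against grid.** Footnote (1) speaks of an every-other-week pattern, but the Vital Signs row also has entries at Weeks 2 and 14. These 2 visits lie outside the pattern, so the documents do not state whether their readings come before or after the dose. Even if the Week 2 reading followed that day's SC dose, it would still be about 7 days after the infusion, and the count of 0 on infusion day would not change.

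**Size of the comparison.** At 2:1 randomization, 9 patients give 6 active and 3 placebo (9 × 1/3 = 3), and 12 give 8 and 4 (12 × 1/3 = 4).

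**The case against.** Four arguments deserve weight.

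1. **Adverse events cover the hours after the infusion.** Section 8.2 collects them from consent to discharge, and they belong to the same primary endpoint. A symptomatic reaction on site would be captured. This stands, and a reader who inferred that the primary safety endpoint is blind to the infusion would be wrong. But Section 8.2 makes an isolated vital-sign finding an adverse event only under conditions such as symptoms, corrective treatment or investigator judgment. A change that nobody measured cannot be appraised.

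2. **Readings may be taken anyway.** Section 5.2.4 on administration is partly redacted and points to a Pharmacy Manual that is not available here. Footnote (1) also cannot be a full list of what is recorded, since it governs adverse events too, and those plainly are not collected only before dosing. So the documents do not support saying that no post-infusion reading will be made. What stands is narrower: none is a scheduled time point. The readable Schedule states exact post-infusion times for PK and none for vital signs, and Section 10.4.5.3 summarises by scheduled time.

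3. **The choice may be deliberate.** Section 1.2 rates the infusion-reaction risk as low, and Section 1.4 reports that 1000 mg IV was well tolerated in Phase 1a on preliminary blinded data, with mild events and none serious. Quoting the TNF result alone would mislead. This lowers the urgency. It does not alter the fact that a named endpoint has no acute value in patients with the disease.

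4. **The gain is small.** With 3 or 4 placebo patients and no tests, two readings after one infusion will be weakly informative. That is true, and a reason to present them descriptively.

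**Conclusion.** The point holds within limits. On the day of the only IV dose, 0 vital-sign readings are scheduled after dosing starts. The next is nominally 7 days later (5 to 9 days with both windows). The controlled summary of a primary endpoint component therefore has no acute post-infusion change, while the patient is on site for PK at 1 h and 2 h.

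A reader might infer more than this from footnote (1). The documents do not support these readings:
- That every vital-sign reading precedes a dose: Weeks 37 and 45 have no dose, and the timing at Weeks 2 and 14 is not stated.
- That nothing is recorded after the infusion: 21 later vital-sign visits are scheduled.
- That the gap should be counted over all 20 dosing visits: 19 are SC.
- That patients go unobserved after the infusion: the documents do not say so, and this point makes no judgment on observation or care.

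The conclusion assumes that the single Week 1 entry is the pre-dose reading that footnote (1) describes, and that no other scheduled time point exists in text not available here. It is a worthwhile, inexpensive improvement to endpoint recording, not a flaw that undermines the trial.

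**What to change.** 1. In Tables 1 and 3, amend the Vital Signs row and footnote (1) so that at IP Week 1 vital signs are also recorded at the two post-infusion PK times of footnote (10).
2. In Section 10.4.5.3 and the SAP, name these two time points and summarise change from the Week 1 pre-dose value by arm, descriptively.
3. If such readings are already taken under the administration text or the Pharmacy Manual, list them in the Schedule as time points so that they enter the summary.
4. In all four tables, reconcile the every-other-week wording of footnote (1) with the vital-sign entries at Weeks 2 and 14, and state their timing relative to the dose.

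**Cost.** Two extra sets of readings per patient, or 9 × 2 = 18 to 12 × 2 = 24 sets for 9 to 12 dosed patients, with no extra visit. The rest period in Section 8.10 has to be fitted around the PK draws. The comparison remains descriptive, on about 3 to 4 placebo patients. The change concerns what is recorded for the endpoint; observation and care rules are left to the sponsor.
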